8.2 HIV DNA Expression Plasmids

[figure not shown]
[figure not shown]
[figure not shown]

[figure not shown]
[figure not shown]

[REDACTED]

[figure not shown]

[figure not shown]
[figure not shown]
[REDACTED]

[figure not shown]
[figure not shown]
[figure not shown]
[figure not shown]
[figure not shown]

8.3 GENEVAX® IL-12 pDNA Vaccine Adjuvant

[figure not shown]
[figure not shown]
[figure not shown]
[figure not shown]

8.4 TDS-IM v1.0 Electroporation Device

[figure not shown]

[REDACTED]

[figure not shown]
[figure not shown]
[REDACTED]

[REDACTED]

[REDACTED]

8.5 MVA62B

8.6 10-1074

[REDACTED]

[REDACTED]

[REDACTED]

[REDACTED]

8.7 VRC07-523LS

[REDACTED]

[REDACTED]

[REDACTED]

[REDACTED]

- [REDACTED]
- [REDACTED]
- [REDACTED]

[REDACTED]

[REDACTED]

[REDACTED]

[REDACTED]

[REDACTED]

[REDACTED]

[REDACTED]

8.8 Lefitolimod

[REDACTED]

[REDACTED]

[REDACTED]

[REDACTED]

[REDACTED]

[REDACTED]

[REDACTED]

[REDACTED]

[REDACTED]

[REDACTED]

9 STUDY PROCEDURES

Prior to conducting any study-related activities, written informed consent and the Health Insurance Portability and Accountability Act (HIPAA) authorization must be signed and dated by the subject.

Blood collection will occur at visits as outlined in the Schedule of Events and will be timed to stay within Red Cross Guidelines (less than approximately 480 mL every 8 weeks).

Given the expected age of our study population (most will likely be at least 50 years old) we expect many participants to have a number of chronic medical conditions, which might change over time. The interval between the screening visit and the first study vaccination will be limited to 60 days.

All subjects will be observed for adverse reactions for at least 30 minutes after administration of any of the study products and at least 4 hours following administration of bNAbs. .

Study specific case report forms will be administered for data collection and clinical assessments as described in Sections 9.1-9.3.

Laboratory personnel and those involved in raw data analysis of the endpoint assays (Sections 9.12-9.15) will be blinded with regards to participant identity and study time point.

9.1 Concomitant Medications

All concomitant medications taken within 30 days prior to screening and entry and a complete history of ART, HIV-1 related vaccines, and immune-based therapies will be documented at the Screening and Entry visits.

At each subsequent visit, all additions or discontinuations of prescription medications should be recorded. Actual or estimated start and stop dates should be recorded.

9.2 Demographics and Medical History

Demographic information (date of birth, sex, race and ethnicity) will be recorded at Screening.

At Screening, the first Baseline visit (B1) and Entry (Day 0), the medical history must include all diagnoses within the past 30 days and, regardless of when the diagnosis was made, a complete history of chronic conditions, malignancies, and AIDS-defining conditions. Self-reported or documented nadir CD4+ T cell count should be recorded.

Any allergies to any medications or their formulations should also be recorded.

9.3 Clinical Assessment

Signs and Symptoms

At pre-entry, all grades of signs and symptoms that occurred 30 days prior to the visit must be recorded.

At entry and all post-entry visits, all grades of signs and symptoms that occurred since the previous visit must be recorded. Duration (start and stop dates and times), severity/grade, outcome, treatment and relation to study drug will be recorded on the study-specific case report form (CRF). Criteria for participant management, dose interruptions, modifications, and discontinuation of treatment will be mandated only for toxicities attributable to the study medication(s).

Diagnoses

All clinical events and new diagnoses or changes in diagnoses should be recorded.

9.4 Physical Examination

Complete Physical Exam

A complete physical examination should be conducted at screening. It is to include at minimum an examination of the skin, head, mouth, and neck, auscultation of the chest, cardiac and abdominal exam, examination of the lower extremities for edema, and Karnofsky performance score. The complete physical exam will also include resting vital signs (temperature, pulse, respiratory rate, and blood pressure), height and weight.

Targeted Physical Exam

A targeted physical examination should be conducted at each subsequent visit following screening. It is to include resting vital signs (temperature, pulse, respiratory rate, blood pressure) and weight, and is to be driven by any new signs or symptoms that the participant has experienced since the last visit.

Eye Exams

Due to rare ocular toxicity reported with bNAb administration, participants will undergo ophthalmologic exams at screening and in the period between Week 12-16 of the ATI (study Weeks 46-50). If a participant discontinues treatment prior to receiving bNAbs a follow-up ophthalmologic exam will not be required. Should premature discontinuation occur after bNAb administration but prior to Weeks 12-16 of the ATI, an ophthalmologic exam will be conducted within 16 weeks of the last bNAb dose. An ophthalmologist affiliated with the study will be available if patients experience ocular symptoms during the course of the study. Ophthalmologic services will be provided by the Department of Ophthalmology at Zuckerberg San Francisco General Hospital. The content of these exams will be at the discretion of the ophthalmologist, but may include dilation of the pupils.

9.5 Clinical Laboratory Measurements

Hematology

Complete blood count (hemoglobin, hematocrit, red blood cell count, white blood cell count, white blood cell differential, and platelet count) will be obtained at screening, the first baseline visit (B1), entry, and all post-entry visits through week 24. CBCs will be obtained every two weeks during W24-34, and then every four weeks through the end of the study.

Chemistry

Serum sodium, potassium, chloride, bicarbonate, random glucose, blood urea nitrogen (BUN), creatinine, aspartate aminotransferase (AST/SGOT), alanine aminotransferase (ALT/SGPT), alkaline phosphatase, total bilirubin, and albumin will be obtained at screening, entry, and most post-entry visits, as detailed in Section 10. Note that total and direct bilirubin will be measured at screen and at all chemistry timepoints from Week 24 onwards.

Pregnancy Testing

A serum or urine β -human chorionic gonadotropin HCG test (urine test must have a sensitivity of 25 mIU/mL) will be obtained from female subjects with reproductive potential at screening and frequently

throughout the study (see Schedule of Events). Specifically, a serum or urine pregnancy test will be performed and reviewed on day of and prior to each study injection during stages 1-3 (DNA vaccines and MVA), prior to administering bNAbs (beginning of Stage 4), and every two weeks during lefitolimod administration (Stage 4), prior to second administration of bNAbs and the ATI (beginning of Stage 5) and every four weeks during the ATI (Stage 5). As of Protocol Version 2.2, no further lefitolimod will be administered.

9.6 HIV Clinical Laboratory Measures

Blood will be obtained and sent to a CLIA-certified or equivalent laboratory for real-time determination of absolute CD4+ and CD8+ T cell counts, percentages, and CD4/CD8 ratio and plasma HIV-1 RNA quantification (viral load) at most visits, as detailed in section 10. All efforts will be made to have collection of blood for T cell counts occur between 8:00 AM and 11:00 AM, in order to account for diurnal variation in CD4+ T cell count.

9.7 Cryopreservation of Plasma

Plasma will be collected and stored at the indicated visits.

9.8 Cryopreservation of PBMCs

PBMCs will be collected and stored at the indicated visits.

9.9 Collection of PAXgene specimen

Whole blood will be collected in PAXgene tubes at the indicated visits.

9.10 Pharmacokinetic Measurements

Broadly neutralizing antibody (10-1074, VRC07-523LS) levels will be measured at indicated visits during Stages 4 and 5. Plasma samples will be collected every 2 weeks for 10 weeks during Stage 4 (bNAbs/lefitolimod) and every two weeks for 24 weeks during the Stage 5 (bNAbs/ATI).

[figure not shown]
[figure not shown]
VRC07 levels will be measured at the Vaccine Immunology Testing Laboratory (VITL) located at the VRC using well-validated assays. Concentrations of VRC07-523LS for the PK analyses will each be measured by qualified ELISAs using a Beckman Biomek based automation platform. Briefly, the VRC07-523LS anti-idiotypic MAb is coated onto Immulon-4HXB microtiter plates overnight at 4° C. Plates are washed and blocked (10% FBS in PBS) for 2 hours at room temperature. Duplicate serial 3-fold dilutions covering the specific range (100 – 218,700) of the test sample are incubated for 2 hours at 37°C followed by horseradish peroxidase - labeled goat anti-human antibody (1 hour, 37° C), and TMB substrate (15 minutes, room temperature). Color development is stopped by addition of sulfuric acid and plates are read within 30 minutes at 450 nm via the Molecular Devices Paradigm plate reader. Linear regression of a standard curve of VRC07-523LS covering the linear range is utilized to quantitate the sample concentrations of each antibody based upon the average of sample dilutions within the range of the assay.

Similarly, 10-1074 levels will be measured at using a validated ELISA; it is expected that these assays will be performed by [name] and her colleagues using a BMGF-funded core laboratory.

9.11 PhenoSense Neutralizing Antibody Assay

Neutralizing antibody susceptibility will be determined using the PhenoSense neutralizing antibody assay platform pioneered by Monogram Biosciences, Laboratory Corporation of America Holdings. This assay

generates HIV pseudovirions that express envelope proteins that are representative of the quasispecies of either the cell-associated HIV DNA or circulating plasma HIV RNA. This will enable the interrogation of neutralizing antibody susceptibility of PBMC-derived virus from aviremic individuals. Procedures are derived from a well-established assay that has been utilized extensively to evaluate autologous and vaccine elicited neutralizing antibody sensitivity of virions pseudotyped with a population of envelope proteins that are representative of the HIV RNA quasispecies in circulating plasma virus from viremic individuals¹⁴⁷.

The assay will be performed in a CLIA/CAP compliant laboratory.

Samples assayed may demonstrate amplification failure due to a low reservoir state or other issues causing assay failure. These are individuals for whom it will be impossible to identify resistance and most experts agree that these individuals are likely to have susceptible virus.

We will implement this exclusion as follows:

For individuals for whom the Monogram PhenoSense assay is unable to make a determination, we will consider this a lack of evidence for resistance. Such individuals will be eligible to participate in the study.

In situations in which a participant has prior data from the Monogram PhenoSense assay available, we will use the prior result regardless of timing as long as the individual has not interrupted therapy for more than 2 weeks between the timepoint of the test and enrollment in the trial. We will define this as continual ART without evidence of plasma HIV RNA elevated above the assay limit of detection, allowing for isolated levels above the limit of detection if they are less than 200 copies/mL (“blips”).

9.12 Cellular Immunologic Measurements

T cell immunogenicity. High-resolution multi-parameter flow cytometric intracellular cytokine staining (ICS) assays will be used to longitudinally monitor the induction, differentiation, and durability of HIV-specific T cell responses in the peripheral blood. PBMCs will be stimulated *in vitro* with peptides from each of the seven CE regions, or peptide pools of overlapping 15mers derived from Gag, Pol, Env, or Nef (using potential T cell epitope peptides, PTE; NIH AIDS Reagent Program). ICS will be performed on two baseline PBMC samples, and these will be compared to newly-generated T cell responses detectable in PBMCs after the electroporations (Week 20), at the peak of the vaccine response (Week 22 of the study, 2 weeks after the MVA boost), pre-ATI (Week 34 of the study, after a dose of bNAbs and 9 weekly lefitolimod injections), at Week 38 and 42 (approximately when bNAb levels are anticipated to become undetectable), and at Week 54.

The focus of our immunogenicity studies will be to measure: (1) the number of new CE-targeted CD4+ and CD8+ T cell responses elicited by therapeutic vaccination, as well as (2) the magnitude, (3) polyfunctionality (number of effector cytokines including IFN- γ , TNF- α , and IL-2 are by responding cells), and (4) cytotoxic phenotype (expression of Perforin, Granzyme B and degranulation as measured by CD107a upregulation) of the CE-targeted responses. Because the vaccine regimen may also stimulate non-CE Gag responses (with the vaccine dose that includes p55 Gag), as well as Pol and/or Env responses (with the MVA62B vaccine), we will assess these broader responses in parallel (with Nef as a negative control).

Tetramer analysis of CD8+ T cell exhaustion phenotype. One of the major goals of HIV therapeutic vaccination is to determine whether it is possible to induce functional HIV-specific CD8+ T cell responses that are not exhausted. At the baseline and peak time points (Week 22 for post-vaccine evaluation and Week 34 for post-lefitolimod/bNAb evaluation), we will characterize in more depth the phenotype and transcriptional state of existing and vaccine-elicited HIV-specific CD8+ T cell responses using MHC Class I tetramers. We will identify and follow longitudinally pre-existing and *de novo* vaccine-induced HIV-specific CD8+ T cell populations before and after vaccination and characterize CD8+ T cell exhaustion in these populations by evaluating the expression of multiple well-established phenotypic markers of exhaustion, as well as their transcriptomic signature (see below).

Innate Immune Cell Phenotypes. Previous studies suggest that treatment with lefitolimod will stimulate innate immune responses (e.g., dendritic cell and monocyte activation) and that bNAbs may stimulate NK cell responses. To evaluate the impact of our proposed regimen on these parameters, we will perform high-dimensional single-cell analysis of longitudinally sampled PBMC specimens using mass cytometry (CyTOF) panels designed to measure the simultaneous expression level of up to 40 different cell surface and intracellular markers on individual cells.

These measurements will be performed at baseline, Week 1, Week 22, after the last vaccination but prior to administration of bNAb/lefitolimod (Week 24), Week 38, Week 42, and Week 54

As of protocol Version 2.2, no further lefitolimod will be administered. Time points for immunologic measurements may be varied for participants not receiving lefitolimod as outlined in prior protocol versions.

9.13 Transcriptomic Measurements

The [name] Laboratory will perform transcriptomic analysis of (1) whole blood (collected in PAXgene tubes) and (2) FACS-sorted tetramer-detectable populations (pre-existing and vaccine-induced) using RNA-Seq methods optimized and validated for whole blood and small cell populations¹⁴⁸ and analyzed using validated bioinformatic pipelines for gene expression analysis. Transcriptomic profiling of longitudinal samples will enable characterization of vaccine and cytokine adjuvants on host gene expression. In addition, consideration of the gene expression data within the context of the aforementioned immunologic measurements will allow us to identify specific host transcriptomic correlates of vaccine responsiveness.

These measurements will be performed at baseline, when peak post-vaccine memory responses are assessed (for tetramer+ cells: Week 22), prior to the administration of lefitolimod/bNAb (for whole blood RNA-Seq: Week 24), prior to ATI (Week 34), and at weeks 38, 42, and 54.

9.14 Antibody Measurements

The [name] Laboratory will perform a suite of antibody functional assays covering a range of effector mechanisms (ADCC, phagocytosis, complement-mediated destruction, neutrophil activation, and dendritic cell uptake) carried out by a diverse set of innate effector cells (monocytes, NK, dendritic cells, and neutrophils) coupled to Systems Biology computational analyses¹⁴⁹. This approach will be utilized to assess antibody functionality induced following therapeutic vaccination. This “Systems Serology” platform co-interrogates the biophysical features (antibody isotype/subclass and glycosylation), with all functional features to define the specific biophysical characteristics of both bulk and HIV-specific antibodies, creating a function:biophysical features map that may point to the specific antibody subpopulations that may 1) serve as biomarkers of enhanced reservoir control or 2) highlight mechanisms by which antibodies can contribute to control of the viral reservoir.

These measurements will be performed at baseline, prior to bNAb administration (at Week 24), and at the end of the trial (End Study visit).

9.15 Virologic Measures

Since the mQVOA only detects intact proviruses that are induced by a single round of stimulation *in vitro* and replicate in MOLT cells¹⁵⁰, the [name] Laboratory will use a novel and scalable multiplex digital droplet PCR assay to measure the *total* number of intact proviruses (the Intact Proviral DNA Assay, IPDA). The IPDA was developed as a rapid and scalable PCR test to precisely quantify latent HIV-1 in infected individuals using a small biological sample¹⁵¹⁻¹⁵³. This approach requires a cell input of 2-5 million CD4+ T cells. This novel assay will allow us to determine the number of infected cells with intact viral genomes in multiple samples from a large number of study participants as well as generally assess the composition of the persistent proviral landscape in each sample.

These virologic measurements will be performed at baseline, Week 24, and Week 54. These measurements will also be performed 24 weeks after re-initiation of ART.

Ultrasensitive qPCR diagnostics will be used to quantify HIV RNA to single-copy levels.

Cell-associated (CA) total RNA¹⁵⁴ and integrated DNA¹⁵⁵ will be quantified using qPCR assays where nucleic acid input is normalized to cell number.

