| | 
curative study will need to enhance such responses. A common approach to enhance these responses is to co-administer an immunomodulatory (such as TLR9 agonist) with bNABs, hence generating a potent NK cell response and the capacity for ADCC.
 |
| STUDY DESIGN | 
A single arm study of twenty HIV-infected adults on effective ART will be performed.
 
All subjects will receive a combination regimen administered during ART and during an analytic treatment interruption. Our strategy has five stages; (1) IL-12 adjuvanted p24CE DNA prime (p24CE/IL-12) at Weeks 0 and 4, (2) IL-12 adjuvanted DNA boost (p24CE plus p55gag) at Week 12, (3) MVA/HIV62B (MVA62B) boost at Week 20, (4) single dose of two bNABs (VRC07-523LS and 10-1074, which target CD4 binding site and V3 loop, respectively) at week 24 with a TLR9 agonist (lefitolimod) administered weekly between Weeks 25 and 33 (9 doses), (5) ATI with single dose of VRC07 and 10-1074 at Week 34 with follow-up off ART through at least Week 46 (expected) and on or off ART (depending on outcome) through Week 86.
 
Stage 1: Subjects will first be vaccinated with IL-12 adjuvanted HIV DNA vaccines expressing 7 unique conserved elements (CE) from p24 (gag). HIV vaccine and IL-12 DNA will be administered by electroporation at Weeks 0 and 4. The goal is to generate responses to conserved regions while avoiding induction or expansion of immunodominant responses to more variable regions.
 
Stage 2: These responses will then be boosted with IL-12 adjuvanted DNA vaccine containing p24CE and full-length gag (p55) at Week 12. This strategy is expected to boost CE-specific T cell response magnitude and breadth.
 
Stage 3: Subjects will receive an MVA boost at Week 20; this vaccine is expected to further boost the CD8+ T cell responses.
 
Stage 4: A single dose of two bNABs (VRC07-523LS and 10-1074) will be administered intravenously at Week 24, with therapeutic levels expected to persist through at least Weeks 32-34. Starting at Week 25 and continuing through Week 33, subjects will receive a series of a TLR9 agonist (lefitolimod), administered weekly by subcutaneous injection. This stage has three goals: to enhance DNA/MVA vaccine responses, to generate potent NK cell responses and to reverse latency (which will allow vaccine-induced T cells and bNABs to reduce the reservoir size).
 
Stage 5: Subjects will discontinue ART at Week 34. An additional dose of the bNABs will be administered on two days prior to treatment interruption. Therapeutic bNAB levels (and continued viral suppression) are expected through at least Week 42. The goal of this
 |

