Based on these studies, we predict that sequential exposure to (a) a highly immunogenic heterologous prime/boost vaccine (DNA/MVA) vaccine, (b) a combination of bNAbs and a TLR9 agonist and (c) bNAb administration during a treatment interruption will reduce the reservoir size during ART and generate robust CD8⁺ T cell and NK cell responses, resulting in sustained and potent control after therapy is interrupted.

We believe that this approach is more likely to be efficacious than a single intervention. For years, scientists have been calling to abandon single intervention cure trials. Just as we learned that single agent ART, and later 2-agent ART (with older agents), was insufficient to control plasma HIV RNA levels, we are at the phase of HIV cure interventions at which a combination approach will likely be necessary to control the virus. We believe that the proposed combination has the potential to prolong the time participants will be off ART compared with each intervention used alone.

[figure not shown]

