3.2 Secondary Objective

- To evaluate the immunogenicity of this this 5-stage regimen
- To evaluate the anti-reservoir activity of this this 5-stage regimen

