5.2 Secondary Endpoint

- Number, magnitude, polyfunctionality, and cytotoxic phenotype of CE-targeted T cell responses elicited by the vaccination and maintained in the peripheral blood throughout the study as measured by intracellular cytokine staining (ICS) after stimulation with CE-derived peptides. Responses to Gag, Pol, Env, and Nef overlapping peptide pools will be evaluated in parallel
- Frequency of circulating CD4+ T cells harboring replication-competent HIV as measured using multiplex digital droplet PCR assay to quantify the total number of intact proviruses CD4+ T cell counts

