10.8 Combination bNAbs and treatment interruption phase (Stage 5)

Week 34:

Staggered Entry into Week 34 (Protocol Version 2.2)

Participants due to enter Stage 5 will have liver function tests checked within 2 weeks prior to their Week 34 visit. If ALT, AST, and total bilirubin meet criteria for grade 1 or higher (AST or ALT 1.25 x upper limit of normal (ULN), total bilirubin 1.1 x ULN), LFTs will be repeated approximately every 1-2 weeks. The team will only proceed with the second bNAb dose and ATI if/once AST, ALT, and total bilirubin are below the grade 1 threshold.

A study physician will perform a targeted hepatobiliary review of symptoms and exam in all participants on the day of and prior to administration of bNAbs. The study team will review all concomitant medications and counsel participants to discontinue any potentially hepatotoxic agents for the duration of the study.

Participants will be staggered for Stage 5 (bNAbs/ATI) entry. One participant will enter Stage 5 initially, with LFTs checked at weeks 1 and 2 following bNAbs/ATI. If these LFTs remain below the grade 1 threshold, two more participants will enter Stage 5 and have LFTs checked 1 and 2 weeks after bNAbs/ATI. If these LFTs remain below the grade 1 threshold, the remaining 2 participants will enter Stage 5.

Study Procedures

Provided that most recent HIV RNA level was below the level of quantification, subjects will take the last dose of antiretroviral drugs on the day before arriving to the clinic for the Week 34 visit. LFTs will also be checked on the day of the bNAb visit, prior to bNAb administration, to obtain a pre-bNAb/ATI baseline measure.

A second infusion of combination bNAbs will be administered at the time ART is discontinued. Subjects will be observed for 4 hours after bNAb administration to assess for immediate adverse events.

A urine or pregnancy test will be performed and evaluated in females of childbearing potential. If the urine pregnancy test is positive, the positive result will be confirmed with a serum pregnancy test. If the serum pregnancy test is positive, the subject will continue ART.

Hematology, plasma HIV RNA levels and CD4+/CD8+ T cell counts will be measured.

Plasma and PBMCs will be collected and cryopreserved. Serum will be collected.

A PAXgene specimen will be collected.

Week 34+1: Subjects will be contacted by telephone to check on symptoms and overall response to the combination bNAbs infusion.

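### No reservoir assay falls between the end of Stage 4 and ART interruption, so the on-ART effect of Stage 4 cannot be separated from Stage 5, rebound and ART restart

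*Combined protocol and SAP*

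**What the plan says.** Section 3.2 lists this secondary objective: "To evaluate the anti-reservoir activity of this this 5-stage regimen". Section 5.2 gives the endpoint as "Frequency of circulating CD4+ T cells harboring replication-competent HIV as measured using multiplex digital droplet PCR assay", without a time point or contrast. Section 15.5 mentions comparing a final value with a pre-treatment value but does not say which visit is final for reservoir measures.

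Section 9.15 sets the assay times: "These virologic measurements will be performed at baseline, Week 24, and Week 54". The next sentence adds: "These measurements will also be performed 24 weeks after re-initiation of ART". Week 34 is not listed. The sentences on single-copy plasma RNA, cell-associated RNA and integrated DNA come after this and carry no times of their own.

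On intent, Section 2.1 predicts that the regimen "will reduce the reservoir size during ART". The synopsis gives as one of three goals of Stage 4 "to reverse latency (which will allow vaccine-induced T cells and bNABs to reduce the reservoir size".

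On specimens, Section 10.8 says of Week 34: "Plasma and PBMCs will be collected and cryopreserved. Serum will be collected". The schedule of events in Section 10.12 adds a large-volume blood draw and optional leukapheresis at that visit. Sections 9.12 and 9.13 already use Week 34 for intracellular cytokine staining, tetramer work and transcriptomics.

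**The concern.** The plan's central reservoir prediction concerns the on-ART period, and Stage 4 is where latency reversal and antibody-mediated killing are meant to act together. The Week 24 sample comes before that step. The next fixed sample, Week 54, is taken long after ART has stopped, when the synopsis expects rebound to have begun.

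A Week 24 to 54 change therefore combines any Stage 4 reduction, any further Stage 5 reduction, possible reseeding during viremia and, for some participants, a few weeks of resumed ART. A real fall by Week 34 could be masked by later viremia. A lack of change at Week 54 would not show whether Stage 4 failed or whether its effect was undone.

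**Working it through.** The documents give no sample size, power or variance for the reservoir endpoint, so there is no figure to reproduce. The check is a time line, followed by a count of what the schedule can identify.

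**Inputs**

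| Item | Value | Source |
|---|---|---|
| IPDA times | baseline, Week 24, Week 54, restart + 24 weeks | 9.15 |
| First antibody dose | Week 24 | 10.7 |
| Lefitolimod, before Version 2.2 | Weeks 25 to 33 | 10.7 |
| Last ART dose | day before the Week 34 visit | 10.8 |
| Assumed end of antibody effect | about ATI Week 12 | 15.4 |
| Durations in the viral-load restart rules | 4, 6, 12 or 24 weeks | 10.9 |
| Maximum time on study | 112 weeks | synopsis |

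**Step 1: where Week 54 falls**

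- Time into the interruption: 54 − 34 = 20 weeks.
- Assumed antibody wane: 34 + 12 = study Week 46.
- Time since the wane: 54 − 46 = 8 weeks.

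**Step 2: who is in which state at Week 54**

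The onset of viremia is my assumption, so a range is shown. Week 42 is the synopsis's minimum for therapeutic antibody levels. Week 46 is the wane assumed in Section 15.4. Week 50 allows four further weeks. Earliest restart = onset + rule duration.

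| Onset of viremia | 4-week rule | 6-week rule | 12-week rule | 24-week rule |
|---|---|---|---|---|
| Week 42 | 46 | 48 | 54 | 66 |
| Week 46 | 50 | 52 | 58 | 70 |
| Week 50 | 54 | 56 | 62 | 74 |

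With onset at Week 46, the Week 54 samples would include people 2 to 4 weeks back on ART (restart at Week 52 or 50), viremic people still off ART, and controllers. Appendix C lets participants opt out of the interruption, so some may never have stopped ART.

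**Step 3: where the post-restart assay falls**

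With onset at Week 46, restart + 24 gives Weeks 74, 76, 82 and 94, all inside 112 weeks. The assay is feasible, but it follows rebound and does not exist for anyone who stays off ART.

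**Step 4: what can be identified**

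Let *a* be the change over Stages 1 to 3, *b* the change over Stage 4 on ART, *c* the change over Stage 5 off ART including rebound, and *d* the change on re-suppression. For someone off ART at Week 54 who restarts later:

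- Week 24 − baseline = *a*
- Week 54 − Week 24 = *b* + *c*
- (restart + 24) − Week 54 = *d*

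That is three independent changes for four unknowns (rank 3), and only the sum *b* + *c* is available. If restart comes before Week 54, part of *d* enters that sum as well. With a Week 34 assay, Week 34 − Week 24 = *b* and Week 54 − Week 34 = *c*, which is four changes (rank 4).

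**Step 5: how many participants this touches**

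Take the planned 20 and assume all interrupt ART. Under the plan's null control rates (15% early, 5% chronic), expected non-controllers are 15 × 0.85 + 5 × 0.95 = 12.75 + 4.75 = 17.5. With 47% control in the early group and 5% in the chronic group, they are 15 × 0.53 + 5 × 0.95 = 7.95 + 4.75 = 12.7. Rebound thus bears on most participants even if the regimen works as powered.

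**The case against.** The strongest reply is that the objective concerns the whole five-stage regimen. The synopsis says Stage 5 is itself meant to continue reducing the reservoir, so a measurement after Stage 5 fits the objective, and a Week 34 endpoint alone would miss that stage. This stands. A reader might infer that the anti-reservoir objective cannot be answered, and the documents do not support that. Baseline to Week 24, both on ART, covers Stages 1 to 3. Baseline to 24 weeks after restart gives an on-ART net change for those who restart.

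A reader might also infer that no on-ART reservoir measurement follows Stage 4. The post-restart assay is one. What is missing is a measurement before ART is interrupted.

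Nor is Week 54 uninterpretable. Viral load is scheduled weekly to Week 58, so Week 54 values can be described by viremia and ART status, and participants with no rebound carry no reseeding from it. Dropping or demoting Week 54 would do harm, because for participants who never restart ART it is the only reservoir measure after Stage 5.

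Two limits on the remedy also stand. Lefitolimod stopped with Version 2.2, so participants differ in what Stage 4 contained. In addition, the Week 34 sample cannot simply be called pre-infusion. Section 4.1 puts the second antibody dose two days ahead of Week 34, while Section 10.8 puts it when ART stops.

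None of this supplies the missing on-ART measurement after Stage 4.

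**Conclusion.** The point holds in a limited form. As scheduled, IPDA cannot separate the on-ART reservoir effect of Stage 4 from Stage 5, rebound and ART restart: three changes for four phases, with the first post-Stage 4 measurement 20 weeks into the interruption. The objective as a whole can still be addressed in part.

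The gap is in the assay list and is recoverable, since Week 34 cells are due to be stored. It is also out of line with the other laboratory work, which uses Week 34 as its pre-interruption point.

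The 8-week figure rests on the wane assumed in Section 15.4, and the restart dates rest on the assumed onset of viremia. The identifiability result depends on neither. In a single-arm study, a Week 24 to 34 contrast estimates the change across Stage 4. It has no concurrent control and cannot apportion the change between the antibodies and lefitolimod.

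**What to change.** 1. Add Week 34 to the IPDA times in Section 9.15, using cells already banked at that visit. The assay needs 2 to 5 million CD4+ T cells.
2. In Section 15.5, name Week 24 to 34 (Stage 4) and baseline to Week 34 (Stages 1 to 4) as the on-ART contrasts, and describe both by lefitolimod exposure.
3. Keep Week 54 and the post-restart assay. Report Week 54 by ART status and viremia, and state that the post-restart contrast applies only to those who restart.
4. State that the same times, including Week 34, apply to cell-associated RNA and integrated DNA.
5. Reconcile Sections 4.1 and 10.8 on when the second antibody infusion is given, and record for each Week 34 sample whether it was drawn before or after that infusion.

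Cost: one extra IPDA per participant, so at most about 20, and fewer if some participants do not reach Week 34. Each further assay type run at Week 34 adds up to the same number. No new visit or procedure is needed, and the sample size is unaffected.
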